## 1. **Administrative Information**

---

### a. **Title**

Effectiveness of osteopathic treatment in patients with nonspecific neck pain.  
Randomized controlled pragmatic clinical trial.

### b. **Trial registration**

Anticipated its registration in ClinicalTrials.gov after its acceptance by the Ethical Committee.

Identifier: PR407 / 18

### c. **Protocol version**

v. 04: 20/11/2018

## 2. Introduction

---

### a. Justification

In Spain cervical pain affects practically 20% of the population annually, while globally it is estimated that between 22% and 77% of the population will suffer cervical pain at some point in their life. Prevalence increases with age, and is more common in women than in men (1.6: 1).

Although the natural evolution of cervical pain tends to improve, the rates of recurrence and chronicity are high. And therefore it becomes an anatomical region of interest in relation to the assessment of the effectiveness and / or effectiveness of the osteopathic therapeutic approach.

Different studies prove the efficacy of various manual therapy techniques applied on the cervical and / or upper dorsal region, suggesting significant positive changes in cervical pain and mobility levels in patients with nonspecific cervical pain.

In this sense, Casanova-Méndez et al showed that the adjustment of high speed and low amplitude, also called "thrust", of the 4th thoracic vertebra (T4) improves mobility and mechanic-sensitivity of the cervical region as well as decreases pain in the same area. All of the improves appears in the short term. On the other hand, Salom et al concluded that dorsal manipulation using the same thrust technique is more effective than manipulation without thrust to reduce chronic mechanical neck pain of bilateral type.

In relation to the study of interventions that include multiple treatment techniques, we can observe in a study by Saavedra et al that the combination of manipulative techniques at the dorsal and cervical level is more effective than the application of a single cervical technique in the improvement of cervical function. In addition, both approaches show a reduction in cervical pain and increase the range of vertebral movement.

In the same line we find the article by Massarachio et al, revealing positive changes in the short term in patients with cervical pain who underwent cervical and dorsal manipulation both in the index of cervical functionality, numerical scale of pain and overall rate of change.

In a recent systematic review and meta-analysis of 2015 carried out by Franke et al. it is suggested that BMT causes clinically relevant effects in pain reduction as well as in functionality in patients with non-specific chronic neck pain.

Taking these studies as a starting point, it is necessary to bear in mind that the reality of the osteopathic approach to the patient is not limited to the use of a single technique, but that the treatment is formed from a set of them. The ultimate goal is to restore mobility and functionality to a specific region, especially taking into account the concepts of individuality and holism.

For this, it is essential to base the treatment on a previous exploration, and there is evidence of a lack of clinical trials with a perspective based on the result of that previous exploration, taking into account again the individuality of the patient and also the clinical criterion of the therapist. This procedure is more realistic with the usual practice.

On the other hand, it is also necessary to evaluate, as different studies conclude, how the application of osteopathic treatment can be conditioned in the final result at different doses.

In this sense, the latest revision of 2017 of the Clinical Practice Guideline for cervical pain indicates that the dose in terms of intensity, frequency and duration are variable and do not allow to transfer it to practice reliably. It adds as a method to find an adequate dose of treatment the combination of an original test of dose descriptions with clinical judgment, taking into account the principles of physical exercise, movement, pain science and patient preferences.

Lastly, two Cochrane reviews show that both manual therapy and exercise therapy are effective in the treatment of patients with cervical pain. Although later a meta-analysis of Fredin et al. (2017) concluded that the combination of manual therapy and exercises does not seem to be more effective than the practice of physical exercise in isolation.

## **b. Goals**

### Main goal:

The effectiveness of osteopathic treatment will be evaluated in comparison with an exercise plan in patients with nonspecific cervical pain.

### Secondary objective:

The result of the treatment applied in different temporal frequencies will be compared.

## **c. Trial Design**

Randomized, pragmatic, double-blind controlled clinical trial.

### 3. **Methods**

---

#### **b. Selection criteria**

##### Inclusion criteria:

The sample will be formed by patients between the ages of 18 and 75 years, who present cervical pain of any intensity and duration, and with a minimum score of 10 points on the Neck Disability Index (NDI).

##### Exclusion criteria:

Patients who present at the time of recruitment other pathologies or elements that may condition cervical pain, such as: acute shoulder tendinopathy, cervical radiculopathy, chronic diseases of general musculoskeletal involvement (Chronic Fatigue Syndrome and / or Fibromyalgia). Similarly, patients suffering from any type of vertiginous syndrome, who have suffered a whiplash in the last year or who are or have been under treatment for cervical pain in the last 3 months will also be excluded.

The taking of anti-inflammatories by the patient is not taken as a measure of exclusion. If the patient is under pharmacological treatment, it will be recorded and will be taken into account as a co-intervention. However, this treatment will not be modified under any circumstances nor will it be grounds for exclusion from the study.

### **c. Interventions**

The test will be carried out with 3 branches (2 experimental + 1 control).

- All groups (1, 2 and 3) will conduct a home-based pattern of combined exercises based on stretching, active anti-resisted exercises and joint mobility exercises focused on the cervico-dorsal and scapulo-thoracic regions. Whose clinical effectiveness has shown significant positive changes in pain levels and cervical functionality.
- The two experimental groups (group 1 and group 2) will also receive Osteopathic Manipulative Treatment (OMT) whose description is detailed below: (description based on the TIDier intervention report guide).

The TMO is a 100% manual intervention that is applied individually with a direct contact between therapist and patient.

- Groups 1 and 2 will receive 3 sessions of BMT.
  - Group 1 will receive 3 sessions with a weekly frequency (with + -2 days of margin: between 5 and 9 days).
  - Group 2 will receive 3 sessions at the rate of one session every 3 weeks (with + -2 days of margin: between 19-23 days).

The clinical experience of the therapists participating in the intervention indicates that 3 sessions could be a sufficient number to achieve changes in the clinic of patients with nonspecific cervical pain and that these may be clinically significant, either immediately after the intervention and in the middle term (1 month post-intervention).

From the same clinical experience it is considered that an interval of between 1 and 3 weeks is the most common during the course of a treatment to a patient with nonspecific neck pain.

Therefore, it is considered necessary to compare whether there may be differences applying a greater or lesser frequency within the most usual range of applied treatment.

#### **d. Procedures**

At the beginning of the 1st session, a battery of questions will be made as an anamnesis with the objective of evidencing possible risk factors at the therapeutic level (see **Appendix 4**. Patient data collection form). The presence of one or more risk factors will suppose the exclusion of the patient from the study.

Next, a brief osteopathic musculoskeletal evaluation will be made to the patient. This exploration will follow a standardized protocol for all patients in the experimental groups (1 and 2).

The tests to be carried out will be:

- Observation (standing patient):
  - Assessment of the anterior projection of the head
  - Assessment of the variation in the physiological curves of the spine
- Active test of the cervical spine with the patient in a sitting position.
  - Flexo-Extension / Rotations / Lateral inclinations
- Segmental test of joint mobility of the cervical and dorsal spine (patient in sitting and supine position)
- Passive mobility test of the cervical spine (patient in the supine position):
  - Flexo-Extension / Rotations / Lateral inclinations

The combination of exercises scheduled at home for all groups is based on the conclusions of different studies, and will consist of:

- Self-resisted active exercise in flexion, rotations and inclinations of the cervical spine.
- Active mobility in its maximum travel (without forcing pain) in flexion, rotations and inclinations of the cervical spine.
- Stretching upper trapezius muscles and scalenes.
- Active mobility in circumferential joints of the glenohoumeral joint, and in flexo-extension of the thoracic spine.

Said guideline will be shown to the patient during the first visit, and will be accompanied by a visual support with the detail so that he remembers it and can do it at his home.

The work schedule will be carried out for 7 weeks, at a rate of 5 sessions per week.

It will be the patient himself who will keep a diary record of the activity carried out during the weeks that the trial lasts. The diary will be facilitated by the therapists, and in it the exercises to be performed will be indicated.

For groups 1 and 2, a total of 3 techniques selected from a list of 7 available techniques common to all centers will be applied in each session. The choice of techniques will be based on the results of the examination performed, the particularities of the patient and the clinical experience of the osteopath. In each

session the techniques can change under the criteria of the osteopath. However, they will always be 3 and always within the list of available techniques.

The TMO techniques that may be applied will be the following:

\*See the full description of the type of techniques in Glossary Of Osteopathic Terminology, 2011

1. Technique of Inhibition of the suboccipital muscles

Objectives: achieve a relaxation in the short muscle that joins the occipital bone with the C1 and C2 vertebrae and associated vascular and neurological structures, as well as alleviating the associated muscular tension through the insertion of the superior fibers of the trapezius muscle in the same region occipital.

2. Functional technique for the middle and deep cervical fascia

Objectives: to relax the fascial and muscular tissues that make up the anterior muscular bundle of the neck that allows a better alignment of the cervical spine in the antero-posterior projection of the head with respect to the thorax.

3. High-speed cervical spine technique (Cervical wheel C1-C6)

4. High-speed technique in the cervico-dorsal junction (prone position)

5. High speed technique in dorsal column (D1-D12) - (Dog Technique)

Objectives for techniques 3, 4 and 5: recover mobility in specific vertebral segments that present somatic dysfunction, as well as influence primary afferent

neurons in the para-spinal tissue, the motor control system and the pain processing.

The term Somatic dysfunction is part of the osteopathic terminology and is defined as "Alterations in the function of the components related to the somatic system: skeletal, articular and myofascial structures and their related vascular, neural and lymphatic elements" 

6. Muscle stretching technique of the diaphragm (supine decubitus) 

Objectives: to reduce muscle tension by allowing better mobility of the thoracic cage and a better balance of the pressures on the thoracic / abdominal cavity. In the same way, better mobility on the cervical spine.

7. Thorax joint mobility technique (long lever) 

Objectives: to improve the mechanics of thoracic mobility, both at the level of the anterior thoracic cage and lateral and posterior, allowing an improvement in the cervical-thoracic mechanical function.

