***THANK YOU FOR COMPLETING THESE QUESTIONS!***

**d. Appendix 4 (Patient data collection form)**

Patient's Name: _____ Sex: _____ Assigned Group: _____ Identification: _____ Age: _____		

Anamnesis Exclusion
 
 
 Discopathy diagnosed - Level: _____
 
 Previous Radiculopathies: _____
 
 Surgical interventions: _____
 
 Osteosynthesis material carrier: _____
 
 Pacemaker carrier
 
 Previous spine fractures - Level: _____
 
 HTA (medicated / unmedicated) - Value: _____
 
 Osteoporosis diagnosed
 
 Rheumatic Diseases: _____
 
 Cancer history: _____
 
 Current medication (corticosteroids) _____ - -
 
 Current medication (anticoagulants) _____ - -
 
 In current treatment or in anticipation of oral implants or orthodontics for the duration of the study.
 
 
MEDICATION: _____ - - _____ - -                  _____ - - _____ - -
		

Expl #1
 Obs: _____ Active T.: _____ Passive T.: _____ Segm T.: _____	
Expl #2
 Obs: _____ Active T.: _____ Passive T.: _____ Segm T.: _____	
Expl #3
 Obs: _____ Active T.: _____ Passive T.: _____ Segm T.: _____

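### Section 3.b says drug treatment is no ground for exclusion, but section 3.d with Appendix 4 excludes patients taking corticosteroids or anticoagulants

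*Protocol*

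**What the plan says.** Three places in the protocol bear on whether a patient taking medication can enter the trial.

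- **Section 3.b, Exclusion criteria.** The list of excluded conditions is open-ended: "Patients who present at the time of recruitment other pathologies or elements that may condition cervical pain, such as", followed by examples. The next paragraph turns to medication. It first says that anti-inflammatory use does not exclude, then widens the subject: "If the patient is under pharmacological treatment, it will be recorded and will be taken into account as a co-intervention". It closes: "However, this treatment will not be modified under any circumstances nor will it be grounds for exclusion from the study".
- **Section 3.d, Procedures.** "At the beginning of the 1st session, a battery of questions will be made as an anamnesis", whose purpose is to reveal risk factors for the treatment. The text refers to Appendix 4 for the questions and adds: "The presence of one or more risk factors will suppose the exclusion of the patient from the study".
- **Appendix 4, Patient data collection form.** Under the label "Anamnesis Exclusion" stand 13 tick-boxes. Two of them begin "Current medication (corticosteroids" and "Current medication (anticoagulants". A separate free-text line for medication follows the list.

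Section 3.b does not mention Appendix 4. Section 3.h (Randomization) makes allocation follow consent and the inclusion criteria, and does not mention the Appendix 4 questions.

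**The concern.** Staff cannot apply both rules to the same patient. Someone taking a corticosteroid or an anticoagulant is admitted by one section, with the drug noted as a co-intervention, and turned away by another. Who is enrolled, and which eligibility criteria the trial can later report, then depends on which text is followed. The Appendix 4 list also serves as a safety screen, so its standing should not be in doubt.

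A second, smaller matter is when the screen takes place. Section 3.d puts it at the first session without saying whether the envelope has been opened by then. The order matters because section 3.h has the same people recruit, assign and treat, and section 3.i says therapists cannot be masked. An exclusion made once the arm is known would be open to influence by that knowledge; one made before cannot be.

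**Working it through.** The point rests on text, so the check is to set the rules side by side and follow one patient through them. The plan has no figure here to reproduce.

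**Step 1. Apply each rule to a patient on a current corticosteroid or anticoagulant who is otherwise eligible.**

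| Place | Rule | Corticosteroid | Anticoagulant |
|---|---|---|---|
| 3.b | Drug treatment is recorded, left unchanged, and does not exclude | Eligible | Eligible |
| 3.d with Appendix 4 | Any one listed factor excludes; both drugs are listed | Excluded | Excluded |

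The results are opposite in both columns.

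**Step 2. Could the two boxes be only the record that 3.b asks for?** No. They stand under the exclusion label, and the form has its own line for recording medication. Section 3.d also attaches exclusion to any single factor.

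**Step 3. Could 3.b be about anti-inflammatories alone?** The paragraph opens with them, but its second sentence speaks of pharmacological treatment without limit, and the closing sentence refers back to that. Even if it were confined to anti-inflammatories, corticosteroids act against inflammation, so that item would still conflict.

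**Step 4. How much of the form is affected?** The 13 boxes are: discopathy, previous radiculopathies, surgery, osteosynthesis material, pacemaker, spine fractures, hypertension, osteoporosis, rheumatic disease, cancer history, corticosteroids, anticoagulants, and dental implants or orthodontics. Two of the 13 exclude on medication as such and so meet the rule in 3.b head-on. The other 11 do not contradict that rule.

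**Step 5. Is the order of screen and allocation stated?** Section 3.d gives the first session; section 3.h gives consent and inclusion criteria. Neither mentions the other step. Section 3.f (Participants Schedule) shows only its heading in the copy at hand, and a figure is not shown, so the order may be given there. The readable text neither states it nor proves that the screen comes after allocation.

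**The case against.** The best defence is that the two texts serve different ends. Section 3.b deals with medicines as co-interventions, that is, with drugs that might affect the neck-pain outcome; Appendix 4 looks for risks of the treatment itself. On that reading the anticoagulant box does not conflict, and only corticosteroids remain doubtful. This has some force, and it is why the conflict is clearest for corticosteroids. But nothing in 3.b limits its wording in that way, and a reader at a centre would have to supply the distinction.

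It can also be said that 3.d links openly to Appendix 4, so the further criteria are disclosed. That stands. A reader might infer from the items not named in 3.b that a second, hidden list is at work. The documents do not support this: the link is explicit, the list in 3.b is open-ended, and all that is missing is a reference from 3.b to the form. Nor does anything show that centres would in fact differ. Section 4 (Ethics) gives information, consent and treatment to the same three researchers.

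The more tempting inference is that patients are removed after randomisation, perhaps only from the manual-treatment arms, so that the comparison is biased. The header of the form has a field for the assigned group, and the examination that follows the anamnesis is described for groups 1 and 2. Neither settles the order. The same form goes on to record three sessions and their adverse effects, so it is filled in over time and the group may be entered later. The examination is restricted to groups 1 and 2 while the anamnesis is not, which favours screening everyone. With the schedule unreadable here, exclusion after allocation is possible but not shown.

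**Conclusion.** The eligibility rule on medication is wrong as written: 3.b and 3.d with Appendix 4 give opposite answers for current corticosteroids and current anticoagulants, 2 of the 13 items on the form. This rests on reading pharmacological treatment in its ordinary, unrestricted sense. On the narrower reading the corticosteroid item still conflicts. All three places are readable, so missing text does not explain it, and eligibility belongs in the protocol, so an analysis plan would not resolve it.

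No bias is demonstrated and no numerical effect is claimed. The documents give no rate at which the form would exclude patients, and any bias between arms would require both that the screen follows allocation and that it works differently between arms. The readable text establishes neither. The order of screen and envelope is a point to state, not an error found. Which medication rule should apply is a clinical decision for the sponsor and is not judged here.

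**What to change.** 1. Reconcile section 3.b, section 3.d and Appendix 4 on medication. The sponsor decides which rule applies and words all three places to match.
2. Have section 3.b refer to the Appendix 4 exclusions, so that there is a single eligibility list.
3. As a safeguard, state in sections 3.d and 3.h that the Appendix 4 screen is completed for every candidate, whatever the arm, before the envelope is opened. If section 3.f already says so, a cross-reference is enough.

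How to handle a patient found ineligible after allocation can be left to the analysis plan.

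The cost is a few sentences of protocol text and, if it is not already done that way, filling in the exclusion part of an existing form before the envelope is opened. It needs no further patients, visits or staff.

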## **e. Variables**

### Main Variable:

- o Neck Disability Index (NDI).

This index is the most used in cervical pain assessments. It is a test of 10 questions with 6 possible answers, which punctuate aspects such as the intensity of cervical pain or the degree of limitation in the main activities of daily life.

The score covers the range of 0 to 50 points, the degree of involvement in cervical functionality being greater the higher the score obtained in the test.

We establish the minimum change to be detected (minimum clinically relevant change) at 5 points. The Spanish version of the NDI will be used, validated by Andrade Ortega,JA et al.

### Secondary Variable:

- o Degree of general quality of life, through the SF-36 health questionnaire.

The data will be reported in the form of a report by the patient himself, who will receive via e-mail (whenever possible) or in printed form the questionnaire to be completed and will deliver to the same centre in which the intervention has been carried out.

Adverse effects: A record of any adverse effects that may be occur during the study, these being detailed in the same patient control sheet (see **Appendix 4**).

[figure not shown]

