
TTm #1    __ / __ / __
 
 
 Suboccipital inhibition
 
 Cervical fascia
 
 High cervical speed (C1-C7)
 
 High speed CT
 
 High back speed (D1-D12)
 
 Stretching diaphragm
 
 Chest joint mobility
 
	
TTm #2    __ / __ / __
 
 
 Suboccipital inhibition
 
 Cervical fascia
 
 High cervical speed (C1-C7)
 
 High speed CT
 
 High back speed (D1-D12)
 
 Stretching diaphragm
 
 Chest joint mobility
 
	
TTm #3    __ / __ / __
 
 
 Suboccipital inhibition
 
 Cervical fascia
 
 High cervical speed (C1-C7)
 
 High speed CT
 
 High back speed (D1-D12)
 
 Stretching diaphragm
 
 Chest joint mobility
 

Adverse Effects
	
Adverse Effects
	
Adverse Effects

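### The adverse-effect form prompts at three treatment contacts in each osteopathic group but at none in the exercise-only group, and has no dedicated prompt after session 3

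*Protocol*

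**What the plan says.** Under Secondary Variable in section 3.e, the Protocol commits to "A record of any adverse effects that may be occur during the study, these being detailed in the same patient control sheet" and points to Appendix 4 as that sheet. The commitment covers the whole study and all patients.

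Appendix 4 is a single form. Its header has a field for "Assigned Group", so it appears to be meant for every arm. Below the screening history come three examination columns (Expl #1 to #3), then three dated treatment columns (TTm #1 to #3), each listing the seven osteopathic techniques as tick boxes. One box labelled "Adverse Effects" sits at the foot of each treatment column. The visible form has no other adverse-effect field.

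Section 3.c limits the manual treatment to two arms: "The two experimental groups (group 1 and group 2) will also receive Osteopathic Manipulative Treatment (OMT". Section 3.d limits the examination in the same way: "This exploration will follow a standardized protocol for all patients in the experimental groups (1 and 2". The home exercises, by contrast, are given to all three groups: "The work schedule will be carried out for 7 weeks, at a rate of 5 sessions per week".

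**The concern.** The rule in section 3.e is general, but the form that carries it out is built around treatment sessions that one arm does not have. If staff follow the form, they are reminded to ask about adverse effects at each osteopathic session and are never reminded to ask a Group 3 patient. All arms exercise, so Group 3 patients can have exercise-related effects as well.

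A harms table by group drawn from this form would then mix two things: how often effects occurred and how often anyone was prompted to write them down. If prompting raises the chance that an effect is recorded, the osteopathic arms would show more events than exercise only even where the true rates were equal. This is a data-collection problem. An effect that was not asked about and not volunteered cannot be recovered by any later analysis.

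**Working it through.** The Protocol gives no figure to reproduce here. The check is a count of form fields, set against the arms and the schedule.

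**Step 1. Adverse-effect boxes on the form (Appendix 4).** One per treatment column, three columns: 3 boxes. The boxes carry no number or date of their own, so their link to a session is read from the column they stand in.

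**Step 2. Prompts by arm (sections 3.c and 3.d).** Prompts = treatment sessions with a column on the form.
- Group 1: 3 sessions, 3 prompts.
- Group 2: 3 sessions, 3 prompts.
- Group 3: 0 sessions, 0 prompts.

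The examination columns do not supply a Group 3 contact either, because section 3.d sets that examination for Groups 1 and 2.

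**Step 3. Prompts after session 3.** No column follows TTm #3, so there are 0 dedicated follow-up prompts in every group.

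**Step 4. Other visible sources of enquiry.**
- Diary (section 3.d): the patient is to "keep a diary record of the activity carried out during the weeks that the trial lasts". It is described as an exercise record, and adverse effects are not mentioned.
- Follow-up (Tracing, section 3.e): schedules the NDI and the SF-36 only.
- NDI and SF-36 (Appendices 2 and 3): neither contains an adverse-effect item.

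Nothing visible fills the gap for Group 3 or for the period after session 3.

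**Step 5. What Group 3 does meanwhile.** 7 weeks × 5 sessions per week = 35 planned home exercise sessions, with no adverse-effect prompt on the form.

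**Step 6. Effect on a comparison.** Let p be the true proportion of patients with an effect in an arm and d the chance that such an effect is recorded. The recorded proportion is p × d, so

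recorded ratio (osteopathic : exercise only) = true ratio × (d osteopathic ÷ d exercise only).

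The last factor equals 1 only if recording is equally complete in both arms. Three prompts against none gives no ground for assuming that. The Protocol gives no value for d, so the size of the distortion cannot be calculated.

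**The case against.** The strongest reply is that nothing in the Protocol restricts recording. Section 3.e covers any adverse effect in the study, the form is shared by all arms, and a Group 3 event or a late event can be written on it. The third box is undated and could take an effect noticed after session 3. In addition, the participant schedule in section 3.f and one figure in section 3.e are not shown, and either might set out further contacts. All of this stands. It limits the point to what the visible form and text prompt for, but it does not make the prompting equal.

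It is also fair to say that the Protocol promises no between-group comparison of harms, and that the NDI and SF-36 results are unaffected.

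Two stronger readings are tempting, and neither is supported.

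- *Days without coverage.* Session 3 falls 2 × (5 to 9) = 10 to 18 days after session 1 in Group 1 and 2 × (19 to 23) = 38 to 46 days in Group 2. Against a 7 × 7 = 49-day exercise programme, a reader might infer 31 to 39, 3 to 11 and 49 days without recording in Groups 1, 2 and 3. That would require exercise to start on the day of session 1, which is plausible because "Said guideline will be shown to the patient during the first visit" but is not stated. It would also require box 3 to close on the day of session 3, which no text says.
- *Bias between Groups 1 and 2.* Both have three prompts at the same three sessions. The different calendar span is the randomised schedule itself, and recording by session is a legitimate choice for a manual treatment.

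**Conclusion.** The point holds as one of unequal prompting: 3, 3 and 0 prompts in Groups 1, 2 and 3, and no dedicated prompt after session 3 in any group. The affected comparison is osteopathic treatment versus exercise only. Counts for that comparison taken from Appendix 4 would partly reflect unequal asking.

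The conclusion rests on reading the boxes as belonging to the columns above them, and on the visible text and form alone. It does not show that any event will be missed, that Group 3 events may not be recorded, or how large the distortion would be. The correction is worth making before recruitment, because the loss cannot be repaired afterwards and the change is small.

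**What to change.** Add one dated adverse-effect question, worded identically for all three groups: any event, its date, its severity and whether care was sought. Send it with the self-reported follow-up questionnaires at time points that are the same in every arm, for example counted from randomisation and including the end of the 7-week exercise programme and the 1-month assessment. Put it on a sheet kept apart from the NDI and SF-36, so that a report of an effect after manipulation does not reveal the allocation to the external investigator on whom section 3.i relies for evaluator masking.

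Name this common question as the source for any comparison of harms with the exercise-only group. Keep the session boxes in Appendix 4 to describe effects after each osteopathic session. If the participant schedule already contains such a contact for all arms, it is enough to say so in section 3.e and add the field to the form.

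The cost is a little more data entry and possibly an extra mailing. The first NDI follow-up is counted from the last session, nominally day 14 + 3 = 17 in Group 1 and day 42 + 3 = 45 in Group 2 with session 1 as day 0, so a common date will not always match an existing contact. Recall over several weeks may also miss brief, minor effects, which is a further reason to keep the session boxes.
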